### 6.3.3 Response Criteria

#### 6.3.3.1 Evaluation of Target Lesions

Complete Response (CR): Disappearance of all target lesions. Any pathological lymph nodes (whether target or non-target) must have reduction in short axis to <10 mm.

Partial Response (PR): At least a 30% decrease in the sum of the diameters of target lesions, taking as reference the baseline sum of diameters.

Progressive Disease (PD): At least a 20% increase in the sum of the diameters of target lesions, taking as reference the smallest sum on study (this includes the baseline sum if that is the smallest on study). In addition to the relative increase of 20%, the sum must also demonstrate an absolute

increase of at least 5 mm. (Note: the appearance of one or more new lesions is also considered progressions).

**Stable Disease (SD):** Neither sufficient shrinkage to qualify for PR nor sufficient increase to qualify for PD, taking as reference the smallest sum of diameters while on study.

#### 6.3.3.2 Evaluation of Non-Target Lesions

**Complete Response (CR):** Disappearance of all non-target lesions and normalization of tumor marker level. All lymph nodes must be non-pathological in size (<10 mm short axis).

Note: If tumor markers are initially above the upper normal limit, they must normalize for a participant to be considered in complete clinical response.

**Non-CR/Non-PD:** Persistence of one or more non-target lesion(s) and/or maintenance of tumor marker level above the normal limits.

**Progressive Disease (PD):** Appearance of one or more new lesions and/or *unequivocal progression* of existing non-target lesions. *Unequivocal progression* should not normally trump target lesion status. It must be representative of overall disease status change, not a single lesion increase.

Although a clear progression of “non-target” lesions only is exceptional, the opinion of the treating physician should prevail in such circumstances, and the progression status should be confirmed at a later time by the review panel (or Principal Investigator).

#### 6.3.3.3 Evaluation of Best Overall Response

The best overall response is the best response recorded from the start of the treatment until disease progression/recurrence (taking as reference for progressive disease the smallest measurements recorded since the treatment started). The participant's best response assignment will depend on the achievement of both measurement and confirmation criteria.

#### For Participants with Measurable Disease (i.e., Target Disease)

Target Lesions	Non-Target Lesions	New Lesions	Overall Response	Best Overall Response when Confirmation is Required*
CR	CR	No	CR	≥ 4 wks. Confirmation**
CR	Non-CR/Non-PD	No	PR	
CR	Not evaluated	No	PR	≥ 4 wks. Confirmation**
PR	Non-CR/Non-PD/not evaluated	No	PR	
SD	Non-CR/Non-PD/not evaluated	No	SD	Documented at least once ≥ 4 wks. from baseline**
PD	Any	Yes or No	PD	
Any	PD***	Yes or No	PD	no prior SD, PR or CR
Any	Any	Yes	PD	

Target Lesions	Non-Target Lesions	New Lesions	Overall Response	Best Overall Response when Confirmation is Required*
*				See RECIST 1.1 manuscript for further details on what is evidence of a new lesion.
**				Only for non-randomized trials with response as primary endpoint.
***				In exceptional circumstances, unequivocal progression in non-target lesions may be accepted as disease progression.
Note:				Participants with a global deterioration of health status requiring discontinuation of treatment without objective evidence of disease progression at that time should be reported as "symptomatic deterioration." Every effort should be made to document the objective progression even after discontinuation of treatment.

### 6.3.4 Duration of Response (DOR)

Duration of overall response: The duration of overall response is measured from the time measurement criteria are met for CR or PR (whichever is first recorded) until the first date that recurrent or progressive disease is objectively documented (taking as reference for progressive disease the smallest measurements recorded since the treatment started).

The duration of overall CR is measured from the time measurement criteria are first met for CR until the first date that progressive disease is objectively documented.

Duration of stable disease: Stable disease is measured from the start of the treatment until the criteria for progression are met, taking as reference the smallest measurements recorded since the treatment started, including the baseline measurements.

### 6.3.5 Progression-Free Survival (PFS)

PFS is defined as the duration of time from start of treatment to time of progression or death, whichever occurs first.

### 6.3.6 Overall survival (OS)

OS is defined as the length of time from start of treatment until death from any cause.

### 6.3.7 Response Review

Tumor measurements will be performed by the CCR radiologist.

## 6.4 TOXICITY CRITERIA

The following adverse event management guidelines are intended to ensure the safety of each participant while on the study. The descriptions and grading scales found in the revised NCI Common Terminology Criteria for Adverse Events (CTCAE) version 5.0 will be utilized for AE reporting. All appropriate treatment areas should have access to a copy of the CTCAE version 5.0. A copy of the CTCAE version 5.0 can be downloaded from the CTEP web site ([http://ctep.cancer.gov/protocolDevelopment/electronic\\_applications/ctc.htm](http://ctep.cancer.gov/protocolDevelopment/electronic_applications/ctc.htm)).

## 7 NIH REPORTING REQUIREMENTS / DATA AND SAFETY MONITORING PLAN

### 7.1 DEFINITIONS

Please refer to definitions provided in Policy 801: Reporting Research Events found at: <https://irbo.nih.gov/hrpp-policy-guidelines/>.

## 7.2 OHSRP OFFICE OF COMPLIANCE AND TRAINING / IRB REPORTING

### 7.2.1 Expedited Reporting

Please refer to the reporting requirements in Policy 801: Reporting Research Events and Policy 802 Non-Compliance Human Subjects Research found at: <https://irbo.nih.gov/hrpp-policy-guidelines/>. Note: Only IND Safety Reports that meet the definition of an unanticipated problem or present new information that might affect the willingness of participants to enroll or remain on the study will need to be reported per these policies.

### 7.2.2 IRB Requirements for PI Reporting at Continuing Review

Please refer to the reporting requirements in Policy 801: Reporting Research Events found at: <https://irbo.nih.gov/hrpp-policy-guidelines/>.

### 7.2.3 NCI Clinical Director Reporting

Problems expeditiously reviewed by the OHSRP in the NIH eIRB system will also be reported to the NCI Clinical Director; therefore, a separate submission for these reports is not necessary.

In addition to those reports, all deaths that occur within 30 days after receiving a research intervention should be reported via email unless they are due to progressive disease.

To report these deaths, please send an email describing the circumstances of the death to [[contact]](mailto:[contact]) within one business day of learning of the death.

## 7.3 NIH REQUIRED DATA AND SAFETY MONITORING PLAN

### 7.3.1 Principal Investigator/Research Team

The clinical research team will meet on a regular basis (weekly) when patients are being actively treated on the trial to discuss each patient. Decisions about dose level enrollment and dose escalation if applicable will be made based on the toxicity data from prior patients.

All data will be collected in a timely manner and reviewed by the PI or a lead AI. Events meeting requirements for expedited reporting as described in Section 7.2.1 will be submitted within the appropriate timelines.

The PI will review adverse event and response data on each patient to ensure safety and data accuracy. The PI will personally conduct or supervise the investigation and provide appropriate delegation of responsibilities to other members of the research staff.

## 8 SPONSOR PROTOCOL/SAFETY REPORTING

### 8.1 DEFINITIONS

#### 8.1.1 Adverse Event

Any untoward medical occurrence in a patient or clinical investigation subject administered a pharmaceutical product and which does not necessarily have a causal relationship with this treatment. An adverse event (AE) can therefore be any unfavorable and unintended sign (including an abnormal laboratory finding), symptom, or disease temporally associated with the use of a medicinal (investigational) product, whether or not related to the medicinal (investigational) product (ICH E6 (R2)).

### **8.1.2 Serious Adverse Event (SAE)**

An adverse event or suspected adverse reaction is considered serious if in the view of the investigator or the sponsor, it results in any of the following:

- Death,
- A life-threatening adverse event (see Section **8.1.3**)
- Inpatient hospitalization or prolongation of existing hospitalization
  - A hospitalization/admission that is pre-planned (i.e., elective or scheduled surgery arranged prior to the start of the study), a planned hospitalization for pre-existing condition, or a procedure required by the protocol, without a serious deterioration in health, is not considered a serious adverse event.
  - A hospitalization/admission that is solely driven by non-medical reasons (e.g., hospitalization for patient or subject convenience) is not considered a serious adverse event.
  - Emergency room visits or stays in observation units that do not result in admission to the hospital would not be considered a serious adverse event. The reason for seeking medical care should be evaluated for meeting one of the other serious criteria.
- Persistent or significant incapacity or substantial disruption of the ability to conduct normal life functions
- A congenital anomaly/birth defect
- Important medical events that may not result in death, be life-threatening, or require hospitalization may be considered a serious adverse drug experience when, based upon appropriate medical judgment, they may jeopardize the patient or subject and may require medical or surgical intervention to prevent one of the outcomes listed in this definition.

### **8.1.3 Life-threatening**

An adverse event or suspected adverse reaction is considered "life-threatening" if, in the view of either the investigator or sponsor, its occurrence places the patient or subject at immediate risk of death. It does not include an adverse event or suspected adverse reaction that, had it occurred in a more severe form, might have caused death. (21CFR312.32)

### **8.1.4 Severity**

The severity of each Adverse Event will be assessed utilizing the CTCAE version 5.

### **8.1.5 Relationship to Study Product**

All AEs will have their relationship to study product assessed using the terms: related or not related.

- Related – There is a reasonable possibility that the study product caused the adverse event. Reasonable possibility means that there is evidence to suggest a causal relationship between the study product and the adverse event.
- Not Related – There is not a reasonable possibility that the administration of the study product caused the event.

## 8.2 ASSESSMENT OF SAFETY EVENTS

AE information collected will include event description, date of onset, assessment of severity and relationship to study product and alternate etiology (if not related to study product), date of resolution of the event, seriousness and outcome. The assessment of severity and relationship to the study product will be done only by those with the training and authority to make a diagnosis and listed on the Form FDA 1572 as the site principal investigator or sub-investigator.

AEs occurring during the collection and reporting period will be documented appropriately regardless of relationship. AEs will be followed through resolution.

SAEs will be:

- Assessed for severity and relationship to study product and alternate etiology (if not related to study product) by a licensed study physician listed on the Form FDA 1572 as the principal investigator or sub-investigator.
- Recorded on the appropriate SAE report form, the medical record and captured in the clinical database.
- Followed through resolution by a licensed study physician listed on the Form FDA 1572 as the principal investigator or sub-investigator.

With the exception of any listed in Section 8.4, reporting is required for all serious adverse events occurring from the first study intervention, Study Day 1, through 30 days after the subject received the last product administration. After 30 days, only adverse events which are serious and related to the study investigational agent need to be reported.

## 8.3 REPORTING OF SERIOUS ADVERSE EVENTS

Any AE that meets protocol-defined serious criteria that require expedited reporting must be submitted immediately (within 24 hours of awareness) to OSRO Safety using the CCR SAE report form. Any exceptions to the expedited reporting requirements are found in Section 8.4.

SAE reports will be submitted to the Center for Cancer Research (CCR) at:

[[contact]](mailto:[contact]) and to the CCR PI and study coordinator. CCR SAE report form and instructions can be found at: <https://nih.sharepoint.com/:u/r/sites/NCI-CCR-OCD-Communications/SitePages/Forms-and-Instructions.aspx?csf=1&web=1&e=uWBXtI>

Following the assessment of the SAE by OSRO, other supporting documentation of the event may be requested by the OSRO Safety and should be provided as soon as possible.

## 8.4 WAIVER OF EXPEDITED REPORTING TO CCR

As disease progression and death are part of the study objectives (OS, PFS, DOR), and captured as an endpoint in this study, they will not be reported in expedited manner to the sponsor. However, if there is evidence suggesting a causal relationship between the study drug and the event, report the event in an expedited manner according to Section 8.3.

## 8.5 SAFETY REPORTING CRITERIA TO THE PHARMACEUTICAL COLLABORATORS

Reporting will be per the collaborative agreement.

## 8.6 REPORTING PREGNANCY

All required pregnancy reports/follow-up to OSRO will be submitted to: [[contact]](mailto:[contact]) and to the CCR PI and study coordinator. Forms and instructions can be found here: <https://nih.sharepoint.com/:u/r/sites/NCI-CCR-OCD-Communications/SitePages/Forms-and-Instructions.aspx?csf=1&web=1&e=uWBXtI>

### 8.6.1 Maternal exposure

Participants should refrain from becoming pregnant during the study and for 6 months after the last dose of SG.

If a participant becomes pregnant during the course of the study, the study treatment should be discontinued immediately, and the pregnancy reported to the Sponsor no later than 24 hours of when the Investigator becomes aware of it. The Investigator should notify the Sponsor no later than 24 hours of when the outcome of the pregnancy becomes known.

Pregnancy itself is not regarded as an SAE. However, congenital abnormalities or birth defects and spontaneous miscarriages that meet serious criteria (Section 8.1.2) should be reported as SAEs.

The outcome of all pregnancies occurring from the date of the first dose of study therapy until 6 months after the last dose of study therapy should be followed up and documented.

## 8.7 REGULATORY REPORTING FOR STUDIES CONDUCTED UNDER CCR-SPONSORED IND

Following notification from the investigator, CCR, the IND sponsor, will report any suspected adverse reaction that is both serious and unexpected. CCR will report an AE as a suspected adverse reaction only if there is evidence to suggest a causal relationship between the study product and the adverse event. CCR will notify FDA and all participating investigators (i.e., all investigators to whom the sponsor is providing drug under its INDs or under any investigator's IND) in an IND safety report of potential serious risks from clinical trials or any other source, as soon as possible, in accordance to 21 CFR Part 312.32.

All serious events will be reported to the FDA at least annually in a summary format.

## 8.8 SPONSOR PROTOCOL DEVIATION REPORTING

A Protocol Deviation is defined as any non-compliance with the clinical trial Protocol, Manual of Operational Procedures (MOP) and other Sponsor approved study related documents, GCP, or protocol-specific procedural requirements on the part of the participant, the Investigator, or the study site staff inclusive of site personnel performing procedures or providing services in support of the clinical trial.

It is the responsibility of the study Staff to document any protocol deviation identified by the Staff or the site Monitor in the CCR Protocol Deviation Tracking System (PDTs) online application. The entries into the PDTs online application should be timely, complete, and maintained per CCR PDTs user requirements.

In addition, any deviation to the protocol should be documented in the participant's source records and reported to the reviewing IRB per their guidelines. OSRO required protocol deviation reporting is consistent with E6(R2) GCP: Integrated Addendum to ICH E6(R1): 4.5 Compliance with Protocol; 5.18.3 (a), and 5.20 Noncompliance; and ICH E3 16.2.2 Protocol deviations.

## **9 CLINICAL MONITORING**

Clinical site monitoring is conducted to ensure:

- that the rights of the participants are protected;
- that the study is implemented per the approved protocol, Good Clinical Practice and standard operating procedures; and
- the quality and integrity of study data and data collection methods are maintained.

Monitoring for this study will be performed by NCI CCR Office of Sponsor and Regulatory Oversight (OSRO) and Regulatory Oversight Support (SROS) Services contractor. Clinical site monitoring activities will be based on OSRO standards, FDA Guidance E6(R2) Good Clinical Practice: Integrated Addendum to ICH E6(R1) March 2018, and applicable regulatory requirements.

Details of clinical site monitoring will be documented in a Clinical Monitoring Plan (CMP) developed by OSRO. CMPs will be protocol-specific, risk-based and tailored to address human subject protections and integrity of the study data. OSRO will determine the intensity and frequency of monitoring based on several factors, including study type, phase, risk, complexity, expected enrollment rate, and any unique attributes of the study and the site. The Sponsor will conduct a periodic review of the CMP to confirm the plan's continued appropriateness. A change to the protocol, significant or pervasive non-compliance with GCP, or the protocol may trigger CMP updates.

OSRO SROS Monitoring visits and related activities will be conducted throughout the life cycle of each protocol. The first activity is before the study starts to conduct a Site Assessment Visit (SAV) (as warranted), followed by a Site Initiation Visit (SIV), Interim Monitoring Visit(s) (IMVs), and a study Close-Out Visit (COV).

Some monitoring activities may be performed remotely, while others will occur at the study site(s). Monitoring visit reports will describe visit activities, observations, and associated action items or follow-up required for resolution of any issues, discrepancies, or deviations. Monitoring reports will be distributed to the study PI, NCI CCR QA, CCR Protocol Support Office, Coordinating Center, and the Sponsor regulatory file.

The site Monitor will inform the study team of any deviations observed during monitoring visits. If unresolved, the Monitor will request that the site Staff enter the deviations in the CCR Protocol Deviation Tracking System (PDTs) for deviation reporting to the Sponsor and as applicable per

## 10 STATISTICAL CONSIDERATIONS

### 10.1 OBJECTIVES AND ENDPOINTS

OBJECTIVES	ENDPOINTS	JUSTIFICATION FOR ENDPOINTS
Primary		
To determine the ORR of SG in participants with recurrent gynecological malignancies, calculated for each individual tumor histology by RECIST v1.1	ORR (RECIST v1.1) assessed by radiographical evaluation i.e., CT/MRI every 9 weeks (+/- 1 week) for the first year and then every 12 weeks (+/- 1 week) until PD or up to 5 years and at EOT which occurs within 14 days after the end of therapy.	Standard endpoint for phase 2 cancer clinical trials. Success of regimens will be determined by these endpoints.
Secondary		
To determine the safety of SG	Identify adverse events (AE) per CTCAE v5.0, by type and grade of toxicity on Days 1, 8, and 15 of each cycle, at EOT which occurs within 14 days after the end of therapy, and 30 days after the end of treatment. Beyond 30 days after the last intervention, only adverse events which are serious and related to the study intervention will be assessed.	Safety is a standard endpoint for clinical trials (collecting information on all major organ function and observed toxicity, if any, to determine prominent toxicity to advise safety).
To determine the PFS of participants receiving SG	Participants will be assessed for PFS by CT CAP at every restaging every 9 weeks for the first year and then every 12 weeks until PD or up to 5 years and at EOT which occurs within 14 days after the end of therapy.	Standard endpoints for correlative studies. These endpoints will explore changes within timepoints as stipulated within the protocol to understand the effect of SG.
To determine the OS of participants receiving SG	Participants will be assessed for OS from start of treatment. OS will be collected on Days 1, 8, and 15 of each cycle for up to 5 years, at EOT which occurs within 14 days after the end of therapy, 30-day safety visit and every 6 months during follow up for up to 10 years.	

OBJECTIVES	ENDPOINTS	JUSTIFICATION FOR ENDPOINTS
To determine the median DoR of SG	Participants will be followed until progression after completion of study therapy and assessed by CT CAP very 9 weeks for the first year and then every 12 weeks until PD or up to 5 years and at EOT which occurs within 14 days after the end of therapy.	
Exploratory		
To evaluate UGT1A1 *28 allele as a predictive marker for gastrointestinal and hematologic toxicities	UGT1A1 allele genotype will be measured at baseline.	UGT1A1 genotype influences the rate of metabolism of SN38 and has been shown to correlate with toxicity in prior trials of SG. This data can guide management of toxicity for participants in this study and future clinical trials.
To evaluate the concordance (or discordance) of TROP2 expression between archival tissues and pretreatment fresh biopsies	The concordance of TROP2 protein expression levels by IHC (median H-scores) between archival tissue samples and fresh pretreatment biopsy	Preclinical data suggest TROP2 expression may change (either decrease or increase) over time but most clinical trials use archival tissue samples to assess TROP2 expression. Our data on the concordance (or discordance) of TROP2 expression between archival and pretreatment samples can help understand SG's biology in participants.
To identify mutations of TROP2 gene ( TACSTD2 ) in tumors with resistance against SG	TROP2 surface protein expression from tumor tissue will be measured at baseline (i.e., prior to study treatment)	Correlates of TROP2 expression, specific transcriptomic, and/or mutational profiles and response can guide appropriate selection of participants in future study if the primary objective is met.

OBJECTIVES	ENDPOINTS	JUSTIFICATION FOR ENDPOINTS
To investigate systemic pharmacodynamic biomarkers before and after SG treatment (i.e., ctDNA, CTC, and $\gamma$ H2AX expression)	Potential PD or predictive biomarker endpoints of DNA damage response pathways from blood will be measured at baseline, C1D8, C3D1, and EOT which occurs within 14 days after the end of therapy and from tumor tissue at baseline and EOT which occurs within 14 days after the end of therapy.	Determine baseline and treatment expression of biomarkers of response.

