## 5 CORRELATIVE STUDIES FOR RESEARCH

### 5.1 BIOSPECIMEN COLLECTION

#### 5.1.1 Sample Collection Table

Test/assay	Type of tube a and volume	Collection point	Location of specimen analysis b
Blood Samples			
Circulating tumor DNA (ctDNA)	2x10mL Streck Tube	C1D1(prior to treatment), C1D8 & C3D1 (within 48 hours after the SG dose), EOT/at progression	Biospecimen Processing Core (BPC)
Circulating tumor cells (CTC)	1x10 mL Streck Tube	C1D1(prior to treatment), C1D8 & C3D1 (within 48 hours after the SG dose), EOT/at progression	DTB Clinical Translational Unit
$\gamma$ H2AX expression	2x8 mL CPT blue/black tube	C1D1(prior to treatment), C1D8 & C3D1 (within 48 hours after the SG dose), EOT/at progression	
UGT1A1 genotyping	1x6 mL Lavender-top tube (K2EDTA)	C1D1 (prior to treatment)	BPC
Tumor Samples			
TROP2 IHC	FFPE , 1 core	Archival FFPE tissue if available, C1D1 (prior to treatment, mandatory except as noted in Section 5.1.3), EOT/at progression (optional) c	BPC/LP
Evaluation of DNA damage repair and other pathway genes (Next gene sequencing, whole genome sequencing and RNAseq)	FFPE/fresh frozen tissues, 3 cores		BPC/fee-for-service Core lab
TSO500	Archival, 10 unstained slides or tissue block	Archival FFPE tissues, C1D1 (prior to treatment)	LP

- a. Please note that tubes and media may be substituted based on availability with the permission of the PI or laboratory investigator.
- b. The location of specimen analysis may be adjusted at the time the analyses are performed
- c. Biopsies may be not performed on the specific dates and times due to the following reasons, including but not limited to, delayed recovery of hematologic toxicities, delayed clinic schedule, or national holidays

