### 5.2.2 Tumor studies

#### 5.2.2.1 TROP2 IHC

TROP2 expression will be assessed by IHC to evaluate concordance (or discordance) between archival tumor tissues and fresh pretreatment biopsy samples. TROP2 IHC will be performed in one representative FFPE tumor section and evaluated independently by two pathologists at CCR/Laboratory of Pathology (LP).

In previous studies, membranous expression is clinically relevant in breast and gynecologic cancers for prognosis and the use of ADC [77, 79, 91, 99, 100]. Therefore, TROP2 expression will be evaluated for membranous expression. Appropriate negative and positive controls will be performed with each case. Protein expression will be quantified using H-score calculated as follows: (1  $\times$  percentage of weak staining) + (2  $\times$  percentage of moderate staining) + (3  $\times$  percentage of strong staining) within the target region, ranging from 0 to 300 [79, 91, 99]. The final immunoreactivity score will be then classified into four ordinal categories: H score 0–9, 10–99, 100–199, and 200–300 groups [79, 91, 99]. For the case where the H scores by two pathologists fall in different H-score groups, the two pathologists review the case together and get a consensus.

Please email to [name], MD PhD at [[contact]](mailto:[contact]) as soon as the participant is scheduled for biopsy.

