### **10.5.8 Exploratory Analyses**

Planned exploratory analyses are detailed in Section [5](#).

Each of these will be done using descriptive methods only and reported as exploratory results. If any statistical tests are performed in these analyses, the results will be presented without adjustment for multiple comparisons but reported in the context of the number of tests performed.

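### The exploratory archival-versus-fresh TROP2 endpoint names only median H-scores; a paired comparison should be specified, because group medians can match when individual participants' samples disagree (minor).

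*Combined protocol and SAP*

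**What the plan says.** Section 10.1 lists the exploratory objective "To evaluate the concordance (or discordance) of TROP2 expression between archival tissues and pretreatment fresh biopsies" and gives its endpoint as "The concordance of TROP2 protein expression levels by IHC (median H-scores) between archival tissue samples and fresh pretreatment biopsy". The justification column adds that expression may fall or rise over time and that most trials rely on archival samples.

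Section 5.2.2.1 repeats the aim: "TROP2 expression will be assessed by IHC to evaluate concordance (or discordance) between archival tumor tissues and fresh pretreatment biopsy samples". It defines a membranous H-score "within the target region, ranging from 0 to 300" and says "The final immunoreactivity score will be then classified into four ordinal categories", with groups 0–9, 10–99, 100–199 and 200–300. Two pathologists read each case. Where their scores "fall in different H-score groups, the two pathologists review the case together and get a consensus". That rule settles differences between readers of one sample; it does not compare archival with fresh tissue.

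Section 10.5.8 refers exploratory analyses back to Section 5 and says "Each of these will be done using descriptive methods only and reported as exploratory results". The sample table in 5.1.1 lists "Archival FFPE tissue if available", so the number of pairs is not fixed. Neither Section 5 nor Section 10 names percent agreement, kappa, an intraclass coefficient, a within-participant difference or a threshold for concordance.

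**The concern.** Concordance is a property of pairs: does this participant's archival score match the same participant's fresh score? A median for each sample type summarises a group and discards the link between the two samples. Opposite changes cancel in the medians, and the justification in 10.1 allows for change in both directions. A report that followed the stated measure literally could describe the samples as concordant when individual scores had moved a long way. What is at stake is the interpretation of one exploratory result, for which a research biopsy is taken from every participant who can safely have one. Fixing the paired summary in advance also avoids choosing an agreement measure after the scores are known.

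**Working it through.** The plan states no sample size, precision or threshold for this endpoint, so there is no figure to reproduce. The check is whether the named measure can separate agreement from disagreement.

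**Inputs.** H-score scale 0–300 and category limits 10, 100 and 200 (5.2.2.1); 22 evaluable participants per cohort and 66 in all as the most pairs (10.3). The scores below are constructed or assumed; the documents give none.

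**Example 1: opposite changes.** Eleven participants go from 50 to 250 and eleven from 250 to 50.
- Archival median = (50 + 250)/2 = 150; fresh median = (50 + 250)/2 = 150.
- Every participant moves between group 10–99 and group 200–300, so 0 of 22 pairs agree.
- Chance agreement = 0.5² + 0.5² = 0.5, so kappa = (0 − 0.5)/(1 − 0.5) = −1.
- Differences are +200 (11 times) and −200 (11 times). Their median is also 0. Their SD is √(22 × 200²/21) = 204.7, so the limits of agreement are 0 ± 1.96 × 204.7, about ±401 points. A median difference therefore needs the limits and the up and down counts beside it.

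**Example 2: scores spread over the scale.** Take 22 archival scores (0, 5, 5, 20, 40, 60, 80, 90, 110, 130, 150, 150, 170, 190, 195, 210, 220, 240, 260, 270, 290, 300). For the fresh scores, swap each of the lower 11 with its counterpart 11 places up (0 with 150, 5 with 170, and so on to 150 with 300).
- Both medians are 150.
- Category counts are 3, 5, 7 and 7. Chance agreement = (9 + 25 + 49 + 49)/484 = 0.273.
- Observed agreement is 0 of 22, so kappa = (0 − 0.273)/(1 − 0.273) = −0.375.
- Mean absolute within-participant difference = 164 points; Lin's concordance coefficient = −0.48.

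**Simulation.** Pairs with equal marginals (assumed uniform on 0–300), varying latent correlation, 66 pairs, 2000 runs each:

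| Latent correlation | Mean difference in medians | Same category | Mean quadratic-weighted kappa |
|---|---|---|---|
| 0 | 0.1 | 31% | 0.00 |
| 0.5 | −0.1 | 45% | 0.42 |
| 0.8 | 0.0 | 61% | 0.70 |
| 0.95 | −0.1 | 80% | 0.86 |

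The expected difference in medians is about zero in every row, from unrelated pairs to near-identical ones. The paired measures separate the rows.

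**Precision of the paired measure.** At correlation 0.8 the middle 95% of simulated weighted kappa runs from 0.55 to 0.81 with 66 pairs and from 0.41 to 0.87 with 22. If scores pile up at the top (assumed 5/5/10/80% across the four categories), 22 pairs give 79% category agreement on average, but weighted kappa averages about 0.58 and ranges from about −0.06 to 0.94.

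**The case against.** The strongest reply is that the noun in the endpoint is concordance and the median appears only in a bracket. A reader might infer that the plan commits to comparing two group medians and so cannot answer its objective. The text does not go that far: no sentence says the medians will be compared, and group medians are the natural reading, not a stated analysis. A median over readers is also possible. Consensus is required only when the two readings fall in different groups; readings of 110 and 190 share a group, so two scores remain to be summarised. On that reading the defect of group medians disappears, but the archival-to-fresh comparison is still unspecified.

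Nor do the documents show that the four categories go unused. They stand in the section that 10.5.8 points to for this analysis; what is missing is the step that sets one sample's category against the other's.

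Two further points stand. The constructed examples have equal medians by design, and uniform scores sit poorly with the high TROP2 positivity reported in 1.2.4, so they show what can happen and do not forecast this trial. And kappa within a cohort would be too imprecise to rely on, so a paired analysis is not free of drawbacks.

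**Conclusion.** The point holds as a minor one. The only measure named for a question about pairs is a group summary on its natural reading, and no other section supplies a paired comparison. That summary can show no difference when every participant has changed category. How likely this is here cannot be judged from the documents, which give neither paired scores nor the number of pairs.

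A reader might infer that the trial's conclusions are at risk. They are not. The endpoint is exploratory and descriptive, TROP2 level is not an eligibility criterion, and no threshold or decision depends on the result. The ORR analysis is unaffected. Scores and categories for each sample are to be collected, so a paired analysis remains possible; the plan does not yet commit to one.

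**What to change.** In 10.1, replace the bracketed median H-scores with a paired description, and state the same in 10.5.8. In participants with both samples, report:
- the number of pairs;
- the cross-tabulation of the four categories in 5.2.2.1, with percent agreement and counts moving up and down;
- the within-participant H-score difference (median, with limits of agreement);
- one weighted kappa or ICC, pooled over cohorts, with a 95% confidence interval.

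Medians per sample type may stay as description. Cohort results should be counts and differences only, without relying on kappa, because a cohort has at most 22 evaluable participants and archival tissue may be missing. It would also help to say how two readings within the same category become one score.

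The cost is a few lines of text and slightly more analysis, with wide intervals to be expected. No new samples are needed, and the change stays within the descriptive approach of 10.5.8.
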